3.3. Secondary Objective

The secondary objective is to determine the association between frequency of medication changes, the PKG information, and other clinical assessments among participants with and without a PKG report of their PD motor status available to the clinician at the time of evaluation.

3.4. Secondary Endpoints

The following secondary clinical outcomes will be measured at and compared between baseline and 4 months follow-up visits.

Secondary clinical outcomes will include:

- 1. Percent “responders” for MDS-UPDRS Total score (based on a minimum clinically important change of >4 points)**

This is a comparison of the percent responders for the within-group change from baseline to 4 months for PKG+ and PKG- groups. This is a comparison of the percent responders for the within-subject change from baseline to 4 months for PKG+ and PKG- groups.

2. Change in motor endpoints from baseline to 4 months including:

a. MDS-UPDRS Part III

- i. Within-subject changes will be calculated as visit value minus baseline value such that a negative change reflects an improvement and positive change signifies a deterioration. Summaries of improved/same/worsened will be provided along with the continuous summaries. (example, 35 (4-month) – 45 (BL))

b. PKG Bradykinesia score (BKS),

- i. Within-subject changes will be calculated as visit value minus baseline value such that a negative change reflects an improvement and positive change signifies a deterioration. Summaries of improved/same/worsened will be provided along with the continuous summaries. (example, 25 (4-month) – 30 (BL))

c. PKG Dyskinesia score (DKS) and measurement of OFF time

- i. Within-subject changes will be calculated as visit value minus baseline value such that a negative change reflects an improvement and positive change signifies a deterioration. Summaries of improved/same/worsened will be provided along with the continuous summaries. (example, 5 (4-month) – 9 (BL))
- ii. Measurement of OFF time will not be included in this analysis

3. Change in PDQ-39 from baseline to 4 months

Change in PDQ-39 from baseline to 4-months. Tabulate values and proportions and changes from baseline to each visit.

Within-subject changes will be calculated as visit value minus baseline value such that a negative change reflects an improvement and positive change signifies a deterioration. Summaries of improved/same/worsened will be provided along with the continuous summaries.

The Parkinson's Disease Questionnaire will be completed by the patient at baseline, 4 months and annual follow-up visits concerning activities in the last month including self-care, walking ability, falling, mental stability, somnolence, etc. This a 5-point scale (never, occasionally, sometimes, often, always). A dimension score is calculated for each of 8 sections and a summary index is then calculated for the entire assessment.

4. Change in MDS-UPDRS Part I from baseline to 4 months

Change in MDS-UPDRS Part I and subsections as noted on the MDS-UPDRS data collection from baseline to 4 months.

Within-subject changes will be calculated as visit value minus baseline value such that a negative change reflects an improvement and positive change signifies a deterioration. Summaries of improved/same/worsened will be provided along with the continuous summaries.

5. Change in MDS-UPDRS Part II from baseline to 4 months

Change in MDS-UPDRS Part II and subsections as noted on the MDS-UPDRS data collection from baseline to 4 months.

Within-subject changes will be calculated as visit value minus baseline value such that a negative change reflects an improvement and positive change signifies a deterioration. Summaries of improved/same/worsened will be provided along with the continuous summaries.

6. Change in MDS-UPDRS Part IV from baseline to 4 months

Change in MDS-UPDRS Part IV and subsections as noted on the MDS-UPDRS data collection from baseline to 4 months.

Within-subject changes will be calculated as visit value minus baseline value such that a negative change reflects an improvement and positive change signifies a deterioration. Summaries of improved/same/worsened will be provided along with the continuous summaries.

7. Change in PKG Scores including BKS, DKS, PTT, FDS and PTI from baseline to 4 months

Change in PKG scores from baseline to interim1, interim 1 to interim2, interim 2 to interim3, interim3 to 4 months for those with interim visits conducted (uncontrolled) or baseline to 4 months for controlled.

Within-subject changes will be calculated as visit value minus baseline value such that a negative change reflects an improvement and positive change signifies a deterioration. Summaries of improved/same/worsened will be provided along with the continuous summaries.

PKG summary scores will be reported on the PKG at baseline, interims (if applicable for those uncontrolled), and 4 months including the following:

- Bradykinesia Score

- Dyskinesia Score
- Fluctuation Score
- Percent Time Immobile (PTI)
- Percent Time Tremor Present (PTT)

Evaluation of individual patient and subgroup response from baseline assessed by change in PKG BK or DK scores from baseline to 4 months for controlled (in target range) and uncontrolled (out of target range) in PKG+ and PKG- groups

- Rate of subjects who were uncontrolled at baseline (PKG Summary Scores exceeded targets) and then became controlled at the 4-month visit (PKG Summary Scores reduced to below targets).
- Rate of subjects unresponsive to medication changes (i.e. no change to PKG BK scores with LED increase)
- Rate of subjects who required treatment changes but were unwilling to make changes (this group may not show any impacts to outcomes)
- Rate of subjects who required treatment changes but were contraindicated to make changes (this group may not show any impacts on outcomes)

8. Change in LED from baseline to each interim visit and 4 months

Calculation of Levodopa Equivalent Dose (LED) at each visit for each patient and a comparison of change in LED at each visit for each patient. If a change is made at the scheduled visit, the change is calculated for the next visit (e.g., a change at the BL visit means the subject has started taking the new medication/dose/frequency change the day after the BL visit, etc.) – See Appendix for reference in calculating LED.

Rate and change in PD medications including medication type, dosing, increase, decrease from baseline to interim1, interim2, interim3, and 4 months.

An analysis to look at medication change amount and frequency and impact on outcome of MDS-UPDRS and PKG BKS will be performed. Patients will be ranked by amount of LED change at each visit and grouped by number of times they had medication changes at a visit (e.g. 0, 1, 2 times, etc.) from baseline to the 4 month visit and correlated to the outcome of MDS-UPDRS and PKG score of BKS at 4 months.

- Rate of subjects who were marked as uncontrolled but had no medication changes will be noted.
- Rate of subjects who had medication changes but were less than 100mg LED will be noted.

9. PKG Patient Survey at 4 months

PKG Patient Survey at 4 months. Tabulate values and proportions and changes from baseline to each visit.

The rate at 4 months will be calculated for the PKG+ and PKG- groups for each section of the survey.

Within-subject changes will be calculated as visit value minus 4-Month value such that a positive change indicates an improvement and a negative change a deterioration. Summaries of improved/same/worsened will be provided along with the continuous summaries.

This assessment is completed by the patient at 4 months.. The assessment contains 2 parts including PKG Use and PKG Impact on Care. The PKG Use is a 5-point scale from strongly disagree to strongly agree concerning PKG training, ease of use, compliance with medication reminders, willingness to use again in PD management. The PKG Impact on Care is a 5-point scale from not valuable to very valuable concerning medication reminders, explanation of symptoms, movement during daily activity and overall value.

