#### 4.5 Interim Follow-Up Visits

Interim follow-ups will be completed for subjects who are not considered to be controlled. For PKG- group subjects, controlled means per clinician standard of care assessment and for PKG+ group subjects, this is per the Acceptable Target Range:

	Target Range
Bradykinesia Score (BKS)	Median BKS 23-25 and/or FDS > 7.5
Dyskinesia Score (DKS)	Median DKS 7-9 and FDS < 13

Interim visits can be completed in-clinic or remotely via telephone per institutional requirements. This timeframe may vary depending on a variety of factors such as physician care practices, amount of total medication change needed, subject medication regimen compliance and subject tolerance to medication changes.

Approximately 28 days prior to each planned subject follow-up visit, a PKG Watch will be ordered through the GKC Portal and dispensed to each subject as previously described and PKG report obtained prior to the visit of PKG+ group subjects for investigator review.

For subjects in the PKG+ Group, the site staff will ensure the PKG is available prior to the Interim Follow-up Visit. Protocol required data collection will occur at each follow-up interim visit. A Subject "ON" State Assessment will be completed and changes in medical history and medications will be recorded. Any protocol defined AEs that have occurred will be captured on the AE Reporting CRF (see Section 8). The study investigator will review the PKG provided by GKC prior to the visit and use the information to guide the discussion with the subject during the clinical assessment. PKG results will be recorded in the PKG Reporting CRF. The study investigator will complete the Clinician Assessment CRF to denote patient-reported symptoms, treatable findings, and clinical management planning based on his/her routine clinical assessment procedures along with the PKG information.

For subjects in the PKG- Group, protocol required data collection will occur at each follow-up interim visit. A Subject "ON" State Assessment will be completed and changes in medical history and medications will be recorded. The study investigator will complete the Clinician Assessment CRF to denote patient-reported symptoms, treatable findings, and clinical management planning based on his/her routine clinical assessment procedures. The study investigator will be blinded to the PKG information during interim visits.

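### SAP 3.4 names no PKG+ versus PKG- estimate or test for the continuous secondary endpoints (items 2-7), and item 7 contradicts itself on the reference visit

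*SAP*

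**What the plan says.** The sentence governing all secondary endpoints in SAP 3.4 reads "The following secondary clinical outcomes will be measured at and compared between baseline and 4 months follow-up visits". Items 2 to 7 (MDS-UPDRS Parts I to IV, BKS, DKS, PDQ-39 and the PKG scores) then carry a common definition: "Within-subject changes will be calculated as visit value minus baseline value such that a negative change reflects an improvement". They add continuous summaries and counts of improved, same and worsened.

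Arms appear in only a few places:
- Item 1 (responders): "This is a comparison of the percent responders for the within-group change from baseline to 4 months for PKG+ and PKG- groups". The sentence is then repeated with within-subject in place of within-group.
- Item 7: a closing paragraph on BKS and DKS response in controlled and uncontrolled subjects of each arm.
- Item 9 (patient survey): "The rate at 4 months will be calculated for the PKG+ and PKG- groups for each section of the survey".

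Item 7 is headed "Change in PKG Scores including BKS, DKS, PTT, FDS and PTI from baseline to 4 months". Its first sentence lists successive visit-to-visit steps, ending "interim3 to 4 months for those with interim visits conducted (uncontrolled) or baseline to 4 months for controlled". The next sentence returns to visit minus baseline.

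The two-sample t-test is named for the primary endpoint only (SAP 3.2; Protocol 6.1 and 6.4). The regression in Protocol 6.4 also has change in Total MDS-UPDRS as its outcome. SAP 5.2 sets a general two-sided 5% level without saying which contrast is tested.

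**The concern.** The main objective (SAP 3.1) asks whether subjects managed with PKG targets do better than those managed by standard of care alone. Only a difference between arms answers that. Both arms are to have medication changes recommended until controlled, so improvement from baseline can be expected in both and does not by itself show a PKG effect. A programmer following SAP 3.4 literally could deliver change from baseline by arm, with or without within-arm p-values, and no treatment difference for any continuous secondary endpoint.

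In item 7, whether a subject contributes steps or a full change depends on having interim visits. That is settled after randomisation. Protocol 4.5 says "For PKG- group subjects, controlled means per clinician standard of care assessment", while PKG+ subjects are judged against the PKG target range. Subsets formed this way are not protected by randomisation, and the quantities computed in them differ.

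**Working it through.** The plan states no power, sample size or effect for any secondary endpoint, so there is no figure to reproduce. The check is mainly of the text.

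**1. Which contrast is named?**

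| Endpoint | Quantity defined | Between-arm estimate or test named |
|---|---|---|
| Primary (SAP 3.2) | change, baseline to 4 months | yes, two-sample t-test |
| Item 1, responders | responder percentage in each arm | comparison implied; no method |
| Items 2-6 | visit minus baseline, per subject | none |
| Item 7, PKG scores | conflicting, see step 2 | none |

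**2. Item 7, three statements together.**
- Heading: baseline to 4 months, with no exception.
- First sentence: step from the previous visit for subjects with interims; baseline to 4 months for controlled subjects.
- Second sentence: visit minus baseline.

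These cannot all be followed. Take the SAP's own BKS example in item 2b, from 30 at baseline to 25 at 4 months. As a change from baseline it is 25 - 30 = -5. If that subject had three interims, item 7's first sentence gives four steps that sum to -5, an average of -5/4 = -1.25 per step. A subject with the same scores and no interims contributes -5. A subject with one or two interims has no listed step ending at 4 months, because the only such step starts from interim 3.

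The conflict is confined to item 7. Items 2b and 2c, and item 7's closing paragraph, already give BKS and DKS from baseline to 4 months. The practical gap is mainly PTT, FDS and PTI.

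**3. Hypothetical illustration of what a within-arm reading risks.** Inputs: SD 13 (SAP 3.2, change in Total MDS-UPDRS); about 20 per arm (41 enrolled, 1:1); an assumed common true improvement m in both arms, so no treatment effect. Suppose each arm's mean change were tested against zero at two-sided 5%, counting significant improvement.

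- Noncentrality = m / (13/√20) = m / 2.907. For m = 5 this is 1.72.
- Critical t on 19 df = 2.093, giving p = 0.372 per arm.
- Exactly one arm significant: 2p(1-p) = 2 × 0.372 × 0.628 = 0.467. PKG+ alone: half of that, 0.234.

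| m (points) | p per arm | exactly one arm significant |
|---|---|---|
| 0 | 0.025 | 5% |
| 2.5 | 0.127 | 22% |
| 5 | 0.372 | 47% |
| 8 | 0.742 | 38% |
| 10 | 0.903 | 17% |

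A between-arm t-test keeps its nominal level throughout. With 20 against 21 subjects and the same SD, its 95% CI half-width is 2.023 × 13 × √(1/20 + 1/21) = 8.2 points, which shows how little 41 subjects can resolve.

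**The case against.** The strongest reply is that visit minus baseline is a derivation, not a test. The primary endpoint is also a change from baseline, and it is compared between arms. The opening of SAP 3.4 may simply be loose wording about visits. A reader might infer that the SAP replaces the randomised comparison with within-arm tests. The text does not support that: it specifies no paired test, no within-arm p-value and no rule based on significance in one arm. The between-arm comparison is unspecified, not displaced.

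Other stronger readings also fail:
- Item 1 is best read as comparing arms. Responder status is itself a change from baseline, so there is no baseline responder rate to set it against.
- The split of reference visit does not run through the secondary endpoints; it is in item 7 alone.
- The trial is not open-label. Both documents call it single-blind, and subjects are blinded to assignment (Protocol 4.4, SAP 4.3).
- The 47% is not this plan's error rate. It assumes tests the SAP does not state, and an SD given for the Total score, which among the SAP's secondary endpoints appears only as a responder rate.

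The Appendix 2 shells might also show columns by arm. That would help, but columns alone do not define an estimate, a method or an interval.

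It can fairly be said that baseline adjustment is a choice, since the primary uses unadjusted change. A between-arm difference in change would also answer the objective. What stands is that no such contrast is written for items 2 to 7, and that item 7 cannot be executed as written.

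**Conclusion.** The point holds in this form. In the visible text, SAP 3.4 names a contrast of visits and gives the continuous secondary endpoints no PKG+ versus PKG- estimate or test, although the main objective is a comparison of arms. Item 7 is also internally inconsistent on the reference visit, in a way that depends on a post-randomisation status defined differently by arm.

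The effect on results cannot be sized from the documents, because no SD is given for any continuous secondary endpoint. The 5% to 47% range only illustrates why separate within-arm results should not stand in for a treatment difference. It rests on 20 evaluable subjects per arm, SD 13 and equal true improvement in both arms. The conclusion about missing methods is limited to the text, since Appendix 2 was not available. This should be corrected, but it does not touch the primary analysis.

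**What to change.** - **Opening of SAP 3.4.** State that each continuous secondary endpoint is reported as the PKG+ minus PKG- difference at 4 months, adjusted for its baseline value (ANCOVA), with a 95% CI. With equal variance at the two visits and correlation ρ between them, adjustment gives about (1 + ρ)/2 of the variance of an unadjusted change comparison, which is useful with 41 subjects.
- **Item 1.** Report the between-arm difference in responder proportions with a CI, and delete the duplicated sentence.
- **Item 7.** Use baseline-to-4-month change for every subject in both arms and for all five scores (BKS, DKS, PTT, FDS, PTI).
- **Labelling.** Mark within-arm and visit-to-visit summaries as descriptive. Bring the Appendix 2 shells into line.

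The cost is SAP wording and table shells. MDS-UPDRS, PDQ-39 and PKG scores are already scheduled at baseline and 4 months, and the watch goes to subjects in both arms. No new data are needed. Subjects lacking either value drop out under the SAP's existing no-imputation rule.

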#### 4.4 Baseline Visit

At 28 days +/- 7 days (21-35 days) after the screening visit, subjects will return to the clinic for the Baseline Visit. For the PKG+ Group, the site staff will ensure the PKG Report is available prior to the Baseline Visit. A subject unable to wear a PKG Watch for at least 6 full days may be exited from the study (complete Study Completion Form) if they are unable to complete a repeat wear of the PKG Watch.

Subjects in both groups will undergo the routine clinical evaluation per standard of care. For all subjects, a medical history update, medication history, and an "ON" state neurological assessment will be completed. Protocol defined adverse events including falls, orthostatic hypotension, bothersome hallucinations, delirium, impairment that prohibits interaction with the PKG watch will be recorded. All subjects will also complete the PDQ-39 questionnaire and MDS-UPDRS. If the MDS-UPDRS is not considered part of the routine clinic visit, the MDS-UPDRS will be conducted for all visits by an independent certified rater.

For subjects in the PKG- Group (SOC control group), protocol required data collection will occur at the baseline visit. A Subject "ON" State Assessment will be completed and changes in medical history and medications will be recorded. The study investigator will complete the Clinician Assessment CRF to denote patient-reported symptoms, treatable findings, and clinical management planning based on his/her routine clinical assessment procedures. The study investigator will be blinded to the PKG information. In this group, the investigator will use clinical history and examination to determine if the subject is "controlled" or "uncontrolled" based on standard of care.

For subjects in the PKG+ Group, the study investigator will review and report on the PKG prior to the visit and use the information to guide the discussion with the subject during the clinical assessment. Subjects will remain blinded to their treatment group so direct reference to the PKG is to be avoided. The PKG will be used to determine if the subject is "controlled" or "uncontrolled" using the consensus-derived target ranges. PKG results will be recorded in the PKG Reporting CRF. The study investigator will complete the Clinician Assessment CRF to denote patient-reported symptoms, treatable findings, and clinical management planning based on his/her routine clinical assessment procedures along with the PKG information.

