These steps will be repeated for each interim follow-up until the study subject is determined to be controlled or a maximum of the 4-month follow-up visit.

Up to 4 medication changes including at the Baseline visit and up to 3 interim visits will be allowed to get each subject into a “controlled” state. Interim follow-up visits end when PD symptoms have become optimized (considered controlled on oral therapies) per standard of care assessments for PKG- group subjects and per the Acceptable Target Range as published in Pahwa et al., 2018 and no further treatment changes are indicated as assessed by the study investigator and the subject will proceed to the next required study visit at 4-months Follow-Up.

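### SAP secondary endpoint 7 splits PKG score change by a controlled/uncontrolled status that is set differently in each group, which leaves the baseline-to-4-month change in FDS, PTT and PTI unclear

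*SAP*

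**What the plan says.** The lead-in to SAP 3.4 has the secondary outcomes "measured at and compared between baseline and 4 months follow-up visits". Item 7 is headed "Change in PKG Scores including BKS, DKS, PTT, FDS and PTI from baseline to 4 months", and Protocol 5.2 lists the same endpoint for all subjects without a split.

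The sentence under that heading names four steps: baseline to interim 1, interim 1 to 2, interim 2 to 3, and interim 3 to 4 months. It assigns them "for those with interim visits conducted (uncontrolled) or baseline to 4 months for controlled". The next paragraph gives a general rule: "Within-subject changes will be calculated as visit value minus baseline value".

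The protocol decides who is controlled, and so who has interim visits. At Baseline (Protocol 4.4), PKG+ subjects are classified "using the consensus-derived target ranges". In the PKG- group, "the investigator will use clinical history and examination to determine if the subject is" controlled or not, and the investigator does not see the PKG. Protocol 4.5 repeats this for interim visits: for PKG- subjects, "controlled means per clinician standard of care assessment and for PKG+ group subjects, this is per the Acceptable Target Range". Ending the interim visits also requires that "no further treatment changes are indicated as assessed by the study investigator".

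**The concern.** A heading promises one quantity for everyone, and the sentence below it delivers different quantities to different subjects. The sorting variable is not a common baseline characteristic. It is a label produced by a PKG rule in one group and by PKG-blind clinical judgment in the other. If results are tabulated as the sentence directs, the uncontrolled rows for PKG+ and PKG- describe differently selected patients, and so do the controlled rows. A reader who sets them side by side is no longer looking at a randomized comparison.

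The sentence also leaves gaps. Two programmers working from it could produce different tables, and one of those tables would lack a 4-month change for some subjects who have both recordings.

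**Working it through.** The plan attaches no figure to this endpoint, so the check is a comparison of the texts.

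**1. What each subject receives under the operative sentence.** Write B for baseline, I1 to I3 for the interim recordings and M for 4 months. The listed steps are I1−B, I2−I1, I3−I2 and M−I3. Protocol 4.5 allows up to three interim visits.

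| Interim visits | Listed steps available | Sum of the steps | Is M−B recoverable? |
|---|---|---|---|
| 0 | none | – | given directly, if controlled |
| 1 | I1−B | I1−B | no; M−I1 is not listed |
| 2 | I1−B, I2−I1 | I2−B | no; M−I2 is not listed |
| 3 | all four | (I1−B)+(I2−I1)+(I3−I2)+(M−I3) = M−B | yes |

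The headed quantity can be rebuilt from the steps only with three interim visits. With one or two, the steps stop before month 4.

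**2. The steps against the change rule.** Visit minus baseline gives I1−B, I2−B, I3−B and M−B. Only I1−B is also in the list of steps. The other three listed steps do not follow the rule, and the SAP text does not say which governs.

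**3. How the sorting status arises.** Randomization is at screening (Protocol 4.3, SAP 4.2). The first controlled/uncontrolled call is at Baseline, 21 to 35 days later (Protocol 4.4).

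- PKG+: PKG target range, with investigator judgment on when interim visits end (Protocol 4.4, 4.5).
- PKG-: clinician assessment, blinded to the PKG (Protocol 4.4, 4.5; SAP 4.3).

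Two identical patients, one per group, can therefore fall in different strata. The SAP uses a common rule elsewhere: the primary-endpoint subgroups in SAP 3.2 define controlled and uncontrolled by the PKG in both groups.

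**4. Which scores depend on this sentence.**

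| Score | Other SAP text giving baseline-to-4-month change |
|---|---|
| BKS | item 2b, unsplit; later paragraph of item 7, split by target range in both groups |
| DKS | item 2c, unsplit; same later paragraph of item 7 |
| FDS | none |
| PTT | none |
| PTI | none |

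Three of the five scores have no second provision in the SAP.

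**The case against.** The best defence is that the surrounding text all points one way. The item heading, the lead-in to SAP 3.4, the visit-minus-baseline rule and the unsplit protocol endpoint each imply a 4-month change for everyone. Item 7 also says scores are reported at baseline, at interims where applicable, and at 4 months, which treats interim values as additions. The labels may merely describe who has interim recordings. Item 7 names no between-group test within strata. The table shells in SAP Appendix 2, which are not among the supplied documents, may settle the matter.

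Most of this stands, and it makes the sponsor's intention fairly clear. It does not remove the conflict: the operative sentence is the most specific instruction in the item, and it says something else.

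A reader might infer three stronger things that the documents do not support:

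- *That baseline-to-4-month change is withheld from all uncontrolled subjects.* For BKS and DKS it is not, as step 4 of the working shows.
- *That the split biases the group comparison by a known amount or in a known direction.* Selecting on a baseline recording can produce regression to the mean. However, FDS has a lower limit (7.5) and an upper limit (13) in the protocol's target table, so the sign depends on which is breached. PTT and PTI are not in the table at all. Any size would only restate assumed reliabilities and correlations.
- *That a given number of the 41 subjects lose their 4-month change.* Interim counts are not reported. The 78% out of target in the earlier cohort (Protocol 1.0) is a PKG figure; it does not tell us how PKG-blind clinicians classify patients or how many interim visits follow.

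It is also fair to say that the Baseline PKG range is itself measured after randomization. The fault lies in the different rule by group more than in the timing.

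**Conclusion.** The point holds as an internal conflict in SAP 3.4 item 7. Read literally, the operative sentence creates strata that are not comparable between groups, omits the last step for subjects with one or two interim visits, and contradicts the item's own change rule. The effect is confined to the 4-month change in FDS, PTT and PTI, within one secondary endpoint of a trial stopped at 41 subjects. The primary ITT comparison does not use this split. No bias size, direction or subject count is claimed.

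The conclusion assumes that the Appendix 2 shells do not already specify the unsplit change. If they do, only the wording needs aligning. Severity is low: an improvement worth making, not a threat to the trial's main result.

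**What to change.** In SAP 3.4 item 7:

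- Define the estimate as 4-month value minus baseline value for BKS, DKS, PTT, FDS and PTI, PKG+ versus PKG-, in all ITT subjects with both recordings, whether or not they had interim visits.
- If results are split by control status, use the Baseline PKG range in both groups, as SAP 3.2 does for the primary-endpoint subgroups.
- Report interim steps as within-group description only, and add the step from the last interim visit to 4 months.

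The cost is a SAP wording change before the 4-month analysis and slightly more tabulation. No new data are needed, because the watch goes to all subjects before Baseline (Protocol 4.3) and before the 4-month visit (Protocol 4.6).
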